#### **10.7 Reporting of adverse drug reactions and other safety information**

All suspected AEs and other safety information associated with the administration of Octagam have to be reported to:

Central Drug Safety Unit:

Email:

[[contact]](mailto:[contact])

[contact]

Serious adverse drug reactions have to be reported immediately by fax or email (within 24 hrs). Non-serious adverse drug reactions and other safety information should be reported to Octapharma, if possible, upon recognition but no later than 10 days.

#### **10.8 Reporting of adverse events to the institutional review board (IRB)**

The principal investigator is required to notify the Sutter Health Institutional Review Committee (SHIRB) of a serious adverse event according to institutional policy.

#### **10.9 Reporting of adverse drug reactions and other safety information to study sponsor**

Octapharma shall notify the Investigator via an IND Safety Report of the following information:

- Any AE associated with the use of study drug in any studies involving Octagam 10% that is both serious and unexpected.
- Any finding from tests in laboratory animals that suggests a significant risk for human subjects including reports of mutagenicity, teratogenicity, or

carcinogenicity.

#### **10.10 Adverse event updates**

The investigator must keep copies of all AE information, including correspondence with Octapharma and the SHIRB, on file.

The investigator shall notify the SHIRB promptly of any new serious and unexpected AE(s) or significant risks to subjects.

### **11 IND REPORTING**

The conduct of the study will comply with all FDA safety reporting requirements.

If the FDA has granted an IND number, it is a requirement of 21 CFR 312.33, that a study completion report is provided to the FDA within 60-days of study completion. 21 CFR 312.33 provides the data elements that are to be submitted in the report. The completion report should be filed in the study's Regulatory Binder, and a copy provided to Octapharma as a supporter of this study as follows:

Octapharma Pharmazeutika Produktionsges.m.b.H  
attn: [name] ([General Manager OPG / Director Int. Drug Regulatory Affairs](#))

[name]  
[name]

All AE reports must include the patient number, age, sex, weight, severity of reaction (mild, moderate, severe), relationship to study drug (probably related, unknown relationship, definitely not related), date and time of administration of test medications and all concomitant medications, and medical treatment provided. The investigator is responsible for evaluating all adverse events to determine whether criteria for "serious" and as defined above are present.

### **12 PROTOCOL DEVIATIONS**

When an emergency occurs that requires a deviation from the protocol for a subject, a deviation will be made only for that subject. A decision will be made as soon as possible to determine whether or not the subject (for whom the deviation from protocol was effected) is to continue in the study. The subject's medical records will completely describe the deviation from the protocol and state the reasons for such deviation. In addition, the Investigator will notify the SHIRB in writing of such deviation from protocol.

Non-emergency minor deviations from the protocol will be permitted with approval of the principal investigator.

### **13 DATA RECORDING, RETENTION, AND MONITORING**

#### **13.1 Data entry and maintenance**

Investigator responsibilities are set out in the ICH guideline for Good Clinical Practice (GCP) and in the US Code of Federal Regulations.

Study personnel will construct case report forms (CRFs), record all study data onto the CRFs and enter the data into a 21 CFR Part 11 compliant database.

### **13.2 Study records retention**

The investigator must ensure that the records and documents pertaining to the conduct of the study and the distribution of the study drug, that is copies of CRFs and source documents (original documents, data, and records [e.g., hospital records; clinical and office charts; laboratory notes; memoranda; subject's diaries or evaluation checklists; SAE reports, pharmacy dispensing records; recorded data from automated instruments; copies or transcriptions certified after verification as being accurate copies; microfiches; photographic negatives, microfilm, or magnetic media; x-rays; subject files; and records kept at the pharmacy, at the laboratories, and at medico-technical departments involved in the clinical study; documents regarding subject treatment and study drug accountability; original signed informed consents, etc.]) be retained by the investigator for as long as needed to comply with national and international regulations (generally 2 years after discontinuing clinical development or after the last marketing approval). The investigator agrees to adhere to the document/records retention procedures by signing the protocol.

### **13.3 Data monitoring committee**

The Data Monitoring Committee (DMC) will be composed of independent reviewers who will meet to review the efficacy and safety data and determine a risk/benefit analysis in this subject population. The purpose of the DMC is to advise on serious safety considerations, lack of efficacy, and any other considerations within the charge to the Committee. The DMC may request additional meetings or safety reports as deemed necessary upon discussion with the investigator or Octapharma and its representatives. The DMC may stop the study following review of results from the interim analysis.

## **14 STATISTICAL ANALYSIS**

### **14.1 Primary endpoint**

Graphs of individual changes in standard uptake ratio values (SURV) of Florbetapir PET will be compared between baseline and 3 months. Graphs of individual changes in RAI values will be compared between baseline and 3 months.

## **15 SAMPLE SIZE**

Five subjects will be included. If it appears that IVIG shows changes in these two markers, a large trial will be considered.

## **16 IMPLICATIONS AND DIRECTION FOR FUTURE STUDIES**

This study will help determine if the reason that IVIG treatment appears to reduce brain atrophy in patients with MCI is due to a reduction of CNS (central nervous system) amyloid levels.

## **17 ETHICAL AND LEGAL ISSUES**

The study will be submitted to the SHIRB. A data safety monitoring committee will be convened to provide oversight of subjects' safety before commencement of the study.

### **17.1 Institutional review board approval**

The protocol for this study has been designed in accordance with the general ethical

principles outlined in the Declaration of Helsinki. The review of this protocol by the SHIRB and the performance of all aspects of the study, including the methods used for obtaining informed consent, must also be in accordance with principles enunciated in the declaration, as well as ICH Guidelines, Title 21 of the Code of Federal Regulations (CFR), Part 50 Protection of Human Subjects and Part 56 Institutional Review Boards.

The investigator will be responsible for preparing documents for submission to the SHIRB and obtaining written approval for this study. The approval will be obtained prior to the initiation of the study.

The approval for both the protocol and informed consent must specify the date of approval, protocol number and version, or amendment number.

Any amendments to the protocol after receipt of SHIRB approval must be submitted by the Investigator to the SHIRB for approval. The Investigator is also responsible for notifying the SHIRB of any serious deviations from the protocol, or anything else that may involve added risk to subjects.

Any advertisements used to recruit subjects for the study must be reviewed and approved by the SHIRB prior to use.

### **17.2 Informed consent**

Informed consent of a subject or his/her designee prior to any study related procedures must be obtained per GCPs as set forth in the CFR and ICH guidelines.

Documentation that informed consent occurred prior to the subject's entry into the study and the informed consent process should be recorded in the subject's source documents. The original consent form signed and dated by the subject and by the person consenting the subject prior to the subject's entry into the study, must be maintained in the investigator's study files.

### **17.3 Subject confidentiality**

Octapharma affirms the subject's right to protection against invasion of privacy. In compliance with United States federal regulations, Octapharma requires the investigator to permit Octapharma representatives and, when necessary, representatives of the FDA or other regulatory authorities to review and/or copy any medical records relevant to the study in accordance with local laws.

Should direct access to medical records require a waiver or authorization separate from the subject's statement of informed consent, it is the responsibility of the Investigator to obtain such permission in writing from the appropriate individual.

### **17.4 Protocol amendments**

Any amendment to this protocol must be agreed to by the principal investigator and reviewed by Octapharma. Amendments should only be submitted to the SHIRB after consideration of Octapharma review. Written verification of SHIRB approval will be obtained before any amendment is implemented.

### **17.5 Premature discontinuation of study**

The responsible local clinical investigator and Octapharma have the right to

discontinue this study at any time for reasonable medical or administrative reasons. Possible reasons for termination of the study could be but are not limited to:

- Unsatisfactory enrollment with respect to quantity or quality.
- Inaccurate or incomplete data collection.
- Falsification of records.
- Failure to adhere to the study protocol.
- Statistical analysis demonstrates overwhelming efficacy of treatment.

Any possible premature discontinuation would be documented adequately with reasons being stated, and information would have to be issued according to local requirements (e.g., SHIRB/EC, regulatory authorities, etc.).

**19 APPENDIX A: NINCDS-ADRDA criteria for diagnosis Alzheimer Disease **

- Dementia established by clinical examination and documented by the Mini-Mental State Test, Blessed Dementia Scale or some similar examination, and confirmed by neuropsychological tests
- Deficits in two or more areas of cognition
- Progressive worsening of memory and other cognitive functions
- No disturbance of consciousness
- Onset between ages 40 and 90, most often after age 65
- Absence of systemic disorders or other brain diseases that in and of themselves could account for the progressive deficits in memory and cognition

*20.0.1     The diagnosis of probable Alzheimer disease is supported by:*

- Progressive deterioration of specific cognitive skills such as language (aphasia), motor skills (apraxia), and perception (agnosia)
- Impaired activities of daily living and altered patterns of behavior
- Family history of similar disorders, particularly if confirmed neuropathologically
- Laboratory results of:
  1. Normal lumbar puncture as evaluated by standard techniques
  2. Normal pattern or nonspecific changes in EEG, such as increased slow-wave activity
  3. Evidence of cerebral atrophy on CT with progression documented by serial Observation

*20.0.2     Other clinical features consistent with the diagnosis of probable Alzheimer disease, after exclusion of causes of dementia other than Alzheimer disease:*

- Plateaus in the progression of the illness
- Associated symptoms of depression, insomnia, incontinence, delusions, illusions, hallucinations; catastrophic verbal, emotional, or physical outbursts, sexual disorders, and weight loss
- Other neurologic abnormalities in some patients, especially with more advanced disease and including motor signs such as increased muscle tone, myoclonus, or gait disorder
- Seizures in advanced disease
- CT normal for age

*20.0.3     Features that make the diagnosis of probable Alzheimer disease uncertain or unlikely include:*

- Sudden, apoplectic onset
  
  - Focal neurologic findings such as hemiparesis, sensory loss, visual field deficits, and incoordination early in the course of the illness
  
  - Seizures or gait disturbances at the onset or very early in the course of the illness
- 20.0.4 5. Criteria for diagnosis of definite Alzheimer disease are:
- The clinical criteria for probable Alzheimer disease and, in addition, histopathological evidence obtained from a biopsy or autopsy.

**23.0 APPENDIX B: Clinical laboratory tests**

Comprehensive Metabolic Panel	Complete Blood Count with differential	Urinalysis
Sodium	WBC	Urine microscopy
Potassium	RBC	Culture if indicated
Chloride	Hemoglobin	
CO2	Hematocrit	
Glucose	MCV	
BUN	MCH	
Creatinine	RDW	
Calcium	Platelet Count	
Total Protein	Neutrophil %	
Albumin	Lymphocytes %	
Total Bilirubin	Monocyte %	
Alkaline Phosphatase	Eosinophil %	
AST	Basophil %	
ALT	Neutrophil Count	
	Lymphocyte Count	
	Monocyte Count	
	Eosinophil Count	
	Basophil Count	

**20 APPENDIX C: INSTRUCTIONS FOR FLORBETAPIR PET**

Imaging will be acquired on a Siemens Biograph mCT (Ultra High-Definition PET/40 slice CT) scanner. Dosing will be 10 mCi Florbetapir in a peripheral vein with saline flush. A 10-minute acquisition will be obtained 30 to 50 minutes after administration. Image data will be processed by iterative reconstruction with all corrections (TOF, PSF modeling, scatter) 256 matrix, 2X zoom, 2.0 Gaussian filter. Images will be interpreted by a radiologist/nuclear medicine physician trained to read Florbetapir studies. Patients with positive studies (moderate to frequent beta amyloid neuritic plaques) will be included in the study and will undergo a repeat Florbetapir PET/CT brain imaging study 3 months later after treatment with either IVIG or placebo.

Analysis: Florbetapir is normally washed out of the cerebellar cortical gray matter in both healthy controls (HC) and in Alzheimer's dementia patients (AD). As such, it is used as the reference region for SUVR calculation. Regions of interest will be drawn around areas of cerebral gray matter in the frontal, lateral temporal, parietal and parieto-occipital regions using the fused PET/CT images and SUVRs will be calculated using the ratio of these SUV values to the value in the cerebellar gray standard uptake value.

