### 3.2 Primary Endpoints

Change in standard uptake values (SURV) as measured by Florbetapir PET at baseline and 3 months and Retinal Amyloid Index (RAI) as measured by amyloid levels in the retina.

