## 4 STUDY PLAN

### 4.1 Study design

This is a single center, open label, proof of concept, out-patient study. Subjects will undergo Florbetapir PET and have retinal amyloid levels measured, receive an infusion of IVIG at 0.4 g/kg every 14 days for a total of five infusions, and repeat PET and retinal amyloid measures three months after the first infusion.

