## 21 APPENDIX D: INSTRUCTIONS FOR RETINAL AMYLOID IMAGING

NeuroVision Imaging, LLC is providing the equipment and software analysis for retinal amyloid imaging.

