### 21.2 Imaging Procedure

The imaging shall use the Retia device with software version 1.4.5 or later.

For each study scan, capture autofluorescence images of the Superior field in 3 focal plans, up to 6 images each

#### a. Image set 1 of 3

- i. First image – Full automatic IR and AFL of superior field.
- ii. Images 2 to up to 6

1. Review the fully automatic IR image and read/record the machine diopter set point (to the tenths digit, e.g. 2.4)

2. Start a new exam, select Superior, and then go to Manual Alignment and Focus mode

a. Use the slider and joystick buttons to enter the previously recorded autofocus value to the nearest tenth of an MD.

b. Use the on-screen buttons and take one IR and then the sequence of 5 AFL images (one every 5 -10 seconds, the LED cycle time).

#### b. Image set 2 of 3

i. Without exiting the exam,

ii. Move the focus point -2 MD using the slider and/or the joystick buttons (e.g. if the initial focus point was 2.4, then move the focus point to 0.4).

iii. Use the on-screen buttons to take one IR and then the sequence of up to 6 AFL images, one every 5 or so seconds.

#### c. Image set 3 of 3

i. Without exiting the exam,

ii. Move the focus point +4 MD (+2 MD from the original recorded focus point, 4.4 in our example here) using the slider and/or the joystick buttons.

iii. Use the on-screen buttons to take one IR and then the sequence of up to 6 AFL images.

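### Appendices C and D do not require masked, shared-outline SUVR measurement or a single retinal software version, so a measurement shift in one marker could pass for an IVIG effect on that marker

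*Combined protocol and SAP*

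**What the plan says.** Section 3.2 defines the PET endpoint as "Change in standard uptake values (SURV) as measured by Florbetapir PET at baseline and 3 months" and adds the Retinal Amyloid Index (RAI). Section 4.1 states: "This is a single center, open label, proof of concept, out-patient study". All subjects receive IVIG. Section 14.1 plans graphs of individual changes and no test. Section 15 sets five subjects and says a large trial will be considered if the two markers appear to change. It gives no threshold and no rule for markers that disagree.

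Appendix C fixes the scanner, injected activity, reconstruction settings, four cortical areas and the cerebellar gray reference. On measurement it says "Regions of interest will be drawn around areas of cerebral gray matter", using the fused PET/CT images. On reading it says "Images will be interpreted by a radiologist/nuclear medicine physician trained to read Florbetapir studies". It does not say who draws the regions. On timing it says "A 10-minute acquisition will be obtained 30 to 50 minutes after administration".

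Appendix D says the vendor "is providing the equipment and software analysis for retinal amyloid imaging". Dilation, retinal field, three focal planes and image counts are specified. On software, Section 21.2 says "The imaging shall use the Retia device with software version 1.4.5 or later".

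Two sets of statements conflict with the rest of the plan. Appendix C places the repeat PET "3 months later after treatment with either IVIG or placebo", and Section 10.1 dates adverse events from randomisation to blinded treatment, although Section 4.1 is open label. Section 8.4 labels Visit 7 as Month 4, whereas the schedule in Section 1 and Sections 4.1 and 4.3 put it at three months.

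**The concern.** The study estimates a before-after change with no control arm, so anything that differs systematically between the first and second scan enters the result in full. Two such sources are left open.

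- **Reader.** The baseline PET must be read at screening for eligibility (Section 5.1), before the follow-up scan exists. Drawing regions separately for each scan, knowing which is which, is a natural way to follow Appendix C. Small differences in where the outlines fall can then track expectation.
- **Software.** A minimum version can be met by two different versions at the two visits. No version at all is fixed for the vendor's RAI scoring.

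At stake is the reading of the graphs in Section 14.1. Section 16 intends the study to help show whether lower amyloid explains why a previous IVIG trial saw less brain atrophy. PET is the direct brain measure, so an error in PET alone could mislead that explanation.

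**Working it through.** **1. Is there a figure to reproduce?** No. Section 15 gives five subjects without alpha, power, effect size or SD. No section gives a scan-rescan SD for SUVR or RAI.

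**2. What is fixed and what is open.**

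| Step | Fixed | Not fixed |
|---|---|---|
| PET acquisition | Scanner, activity, reconstruction, time window | Same start time on both scans |
| PET measurement | Four areas, reference region, fused images | Who draws, masking to scan order, same outlines on both scans |
| Retinal capture | Dilation, field, focal planes, minimum version | Same version at both visits |
| Retinal scoring | Done with vendor software | Version, masking to visit |

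No other section fills the right-hand column.

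**3. Why a shift cannot be separated.** For one marker, observed change = drug effect + natural change + reader or software shift + random error. With one arm, only the sum is observed.

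**4. Illustration of size.** Assumptions, none from the documents: no true change, independent symmetric normal errors, and a common downward shift of b SDs of the individual change. Each subject then falls with probability p = Φ(b).

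- All five fall on one marker: p⁵
- At least four of five fall: p⁵ + 5p⁴(1 − p)
- All five fall on both markers, independent, only one shifted: p⁵ × 0.5⁵ = p⁵/32

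| b | p | All five, one marker | At least four, one marker | All five, both markers |
|---|---|---|---|---|
| 0 | 0.5 | 3.1% | 18.8% | 0.1% |
| 0.25 | 0.5987 | 7.7% | 33.5% | 0.2% |
| 0.5 | 0.6915 | 15.8% | 51.1% | 0.5% |
| 1 | 0.84134 | 42.2% | 81.9% | 1.3% |

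For example, at b = 0.5: 0.6915⁵ = 0.158, and 0.158/32 = 0.005. The protocol states no four-of-five or five-of-five rule; these are ways of describing a graph that looks consistent.

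**5. PET start times.** If the whole 10-minute frame must lie within 30 to 50 minutes, starts range from 30 to 40, so two scans can differ by up to 10 minutes. If the window refers to the start, the difference can reach 50 − 30 = 20 minutes. The documents do not allow this to be turned into an SUVR difference, and they do not show whether it would be random or directional.

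**6. Visit 7 timing.** Take a month as 30.44 days and the ±7 day window.

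- Month 3 from Day 1: 91.3 ± 7, about days 84 to 98.
- Month 4 from Day 1: 121.8 ± 7, about days 115 to 129. No overlap.
- Month 4 from a Day −28 screening start: 121.8 − 28 = 93.8 ± 7, about days 87 to 101. This overlaps days 84 to 98.

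Section 4.3 counts screening in a total of about four months, so the third reading is possible.

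**The case against.** The strongest case against runs as follows. This is a five-subject proof of concept analysed by graphs, whose only stated consequence is that a larger trial will be considered. Acquisition is already well standardised on both markers. The shift is hypothetical and of unknown size. Section 15 speaks of both markers, and a shift in one alone raises the illustrated false signal on both from 0.1% to at most 1.3%. Even perfect masking would leave natural change and scan-rescan noise mixed with any drug effect.

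Much of this stands, and it limits the point to an inexpensive improvement. It does not remove it: Section 15 writes no agreement rule, each marker is a primary endpoint, and a misleading graph for one of them is a result in itself.

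A reader might infer more than the documents support:

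- **That readers will be unmasked or that the software will change.** The text permits both and states neither.
- **That PET timing differences add only noise.** The documents do not say how start times would vary between visits, so neither noise nor bias is shown.
- **That the Month 3 and Month 4 windows cannot overlap.** This holds only if Month 4 is counted from Day 1.

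**Conclusion.** The gap is real. Followed as written, the plan allows a reader or software shift between a subject's two scans that cannot be told apart from an IVIG effect on that marker. This rests on the absence of a comparator and on silence in Appendices C and D about masking, shared outlines and a single version. Its size is not known; the percentages above depend on assumed shifts, independence and normal errors. The main risk is a misleading picture for one marker. An error in one marker alone is unlikely to produce a false signal on both. The placebo, randomisation and Month 4 wording is a separate matter of reconciling the text and adds no weight to the measurement point.

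**What to change.** **Appendix C.** Draw one region set per subject on the CT, following anatomy and not baseline uptake, since outlines fitted to baseline hot spots could themselves produce an apparent fall. Co-register the set to both PET scans. Measure each subject's pair together, in random order and masked to scan date, and name who does this. Leave the baseline eligibility read as it is. Start the follow-up acquisition at about the same minutes after injection as at baseline, and record both times.

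**Appendix D.** Use one capture version for both of a subject's scans where possible. Have the vendor score both visits with one locked version, masked to visit. This requires that the images be kept.

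**Separately.** Reconcile the placebo wording in Appendix C and the randomisation wording in Section 10.1 with Section 4.1. Reconcile Month 4 in Section 8.4 with the three-month visit in Sections 1, 4.1 and 4.3, and state the day from which the visit is counted.

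**Cost.** No extra scan or patient. It takes relabelling, co-registration, scheduling care and vendor cooperation. SUVR values come later, once a pair is complete; pairs complete by any interim analysis under Section 13.3 can be measured the same way. With five subjects a reader may recognise a scan, so masking is imperfect; the shared outlines limit what recognition can change. None of this supplies a comparator or a decision threshold.
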